- ii) It is at the end stage of important functional organ diseases, such as malignant tumors, cardiac failure, etc.
- iii) Limb dysfunction.
- iv) Diagnosed with dementia.

Withdrawal criteria:

- i) Withdrawal of consent by the participant.
- ii) Non-compliance with study requirements (e.g., missing >25% sessions).
- iii) Significant health deterioration affecting participation.

5) Study groups

Experimental group: Older adults with MCI from Jinzhou Rehabilitation Hospital (JRH), with psychomotor rehabilitation nursing plan.

Control group: Older adults with MCI from Jinzhou Pension Comprehensive Service Center (JPCSC), without psychomotor rehabilitation nursing plan.

6) Operational definition:

- i) Mild cognitive impairment (MCI): Mild Cognitive Impairment (MCI) is defined as a condition characterized by noticeable cognitive decline beyond what is expected for an individual's age and education level, but not severe enough to interfere significantly with daily life or independent functioning. It serves as an intermediate stage between normal aging and dementia. (Petersen, R.C., 2004; B. Winblad, 2004).
- ii) Psychomotor therapy (PMT): Psychomotor therapy is a form of therapeutic intervention that focuses on the connection between psychological and motor (physical) functions (Duan Zhouying, Chen Wenhua, 2021).

7) Sample size determination

Objective No. 1 and 2: To develop and validate the psychomotor rehabilitation nursing plan through content/face validation using the Delphi method for older adults with mild cognitive impairment in promoting cognitive function.

A sample size of 8 to 15 respondents has been recommended for Delphi studies, given that smaller samples reduce reliability and bigger ones do not appear to add much value (Kenney et al., 2010). For this study, we aimed to recruit 10-12 participants.

Objective No. 3: To determine the effectiveness of the psychomotor rehabilitation nursing plan in enhancing cognitive function among older adults with mild cognitive impairment .

The sample size was calculated for specific objective 2. It was estimated by using the sample size formula compared with the average of two samples (Ni Ping et al., 2010) . The sample size calculation formula and parameters were as below:

$$N1 = N2 = 2[(t_{\alpha/2} + t_{\beta})S/\delta]^2$$

N1 is the sample content of the experimental group.

N2 is the sample content of the control group.

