S is the estimated value of the standard deviation between the two populations.

δ is the difference between the two averages.

The S and δ were the values of the MMSE scale decided by the researcher based on expert opinion (Liang Jingzhao, Zhi Yanmin, 2022), S= 2.75 , δ = 2.14. The level of significance (α) was 0.05, $t_{0.05/2}= 1.96$, β was 0.10, $t_{0.1}= 1.28$. By substituting the formula, 34 samples were required for each of the two groups.

An estimated 10% was added to the calculated sample size in anticipation of some missing data. The calculated sample size for this study was 76 patients (EG: 38 patients, CG: 38 patients).

8) Sampling method: Purposive sampling

9) Subject setting and participant

PHASE 1 (Delphi-method study for screening and recruitment)

The psychomotor rehabilitation nursing plan design will use Delphi-method which is an integration involving multiple expertise for the PMT development. The participants are the professionals with academic and/or practical experience in Neurology and cognitive training in China's hospitals or universities. There is no agreed method to consider someone an expert in a given field. To facilitate the selection process, it will use a simple point evaluation system. It will include all professionals with a final evaluation of at least 2 points. Regarding academic experience, it will consider the following factors: At least one publication on the

field of cognitive training (1 point) & at least one publication on the field of Neurology (1 point) OR at least one publication on the field of cognitive training in MCI (2 points). Concerning practical experience, it will consider experience in the development of a cognitive training program (1 point). Moreover, it will also consider if the professional had clinical experience in the application of cognitive training (1 point).

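### The plan's sample-size formula gives 34.67 per group, which rounds up to 35, not the stated 34; the effect on power is minor

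*Combined protocol and SAP*

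**What the plan says.** All of this is in the combined protocol and SAP. Item 7, Sample size determination, Objective No. 3, uses the usual formula for comparing two independent means with equal groups: n per group = 2[(t_α/2 + t_β)S/δ]².

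- On the inputs, it says "The level of significance (α) was 0.05", with a quantile of 1.96. β is 0.10, with a quantile of 1.28, so the intended power is 90%.
- The standard deviation and difference are given as "S= 2.75 , δ = 2.14". Their origin is described as follows: "The S and δ were the values of the MMSE scale decided by the researcher based on expert opinion".
- The result is: "By substituting the formula, 34 samples were required for each of the two groups".
- Ten per cent is then added for missing data, and the section concludes: "The calculated sample size for this study was 76 patients (EG: 38 patients, CG: 38 patients".

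Elsewhere, item 10 (Data collection and Research tool) names MoCA as the cognitive scale, and item 11 (Data analysis) names a paired t-test for comparing scale scores.

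**The concern.** Anyone who substitutes the printed values into the printed formula gets 34.67, not 34. The result of a power calculation is the smallest number that meets the target, so a fraction is rounded up. Rounding to the nearest integer also gives 35.

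The stated requirement therefore falls just short of its own criterion, and the 10% is added to that figure to reach the enrolment target. The sample-size statement is normally carried into the report, where the mismatch would be easy to find. At stake is whether the stated requirement and the stated 90% power agree with each other. No analysis or conclusion depends on it.

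**Working it through.** **Inputs** (item 7, Objective No. 3): S = 2.75; δ = 2.14; quantiles 1.96 (two-sided α = 0.05) and 1.28 (β = 0.10); allowance 10%; stated 34 per group, then 38 per group and 76 in total.

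**Step 1. The plan's own formula.**

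- (1.96 + 1.28) × 2.75 / 2.14 = 8.91 / 2.14 = 4.1636
- n = 2 × 4.1636² = 34.67 per group, rounded up to 35

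Unrounded normal quantiles give 34.70, again 35. A one-sided α gives 28.3, so a different choice of sidedness does not explain 34.

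**Step 2. The 10% allowance.** The plan does not say whether it multiplies by 1.1 or divides by 0.9, so both are shown.

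| Start (per group) | × 1.1 | ÷ 0.9 | Rounded up | Total |
|---|---|---|---|---|
| 34 (stated) | 37.4 | 37.8 | 38 | 76 |
| 34.67 (unrounded) | 38.1 | 38.5 | 39 | 78 |
| 35 (rounded up) | 38.5 | 38.9 | 39 | 78 |

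The planned 38 is reproduced from 34. In the other direction, 38 less 10% is 34.2, below 34.67, so the allowance does not absorb the truncation.

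**Step 3. Power under the same S and δ, for a two-sided comparison of two independent groups.** The normal approximation is Φ(δ / (S√(2/n)) − 1.96). The t-test column uses the noncentral t distribution with 2n − 2 degrees of freedom and noncentrality (δ/S)√(n/2).

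| Evaluable per group | Normal approximation | Two-sample t-test |
|---|---|---|
| 34 | 89.4% | 88.5% |
| 35 | 90.2% | 89.4% |
| 36 | 91.0% | 90.3% |
| 38 | 92.4% | 91.7% |

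With 34 evaluable per group, the shortfall from 90% is 0.6 points (normal) or 1.5 points (t-test).

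**Step 4. Loss that the 38 can bear.** By the plan's formula, 38 covers a loss of 38 − 35 = 3 per group, or 3/38 = 7.9%. By the t-test it covers 38 − 36 = 2 per group, or 2/38 = 5.3%. Both are below the 10% budgeted.

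**Note on the quantiles.** The formula is written with t symbols, but 1.96 and 1.28 are standard normal values. Exact t-test power first reaches 90% at 36 per group, so the approximation costs about one participant per group.

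**The case against.** The strongest reply is that the slip is too small to matter. It is one participant per group, and enrolment is 38, not 34. If nobody is lost, power exceeds 90% by either method. By the t-test it is still 90.3% after two losses per group; by the normal approximation it is still 90.2% after three. S and δ are themselves judgements: the formula falls to 34 or below if S is 2.72 instead of 2.75 (33.92), or if δ is 2.17 instead of 2.14 (33.72). The disputed participant lies well inside that uncertainty.

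This stands as an argument about size, and it is why the target need not change. It does not make 34 the answer to the printed formula, and the scenario in which power dips below 90% is the 10% loss that the plan itself budgets for.

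One could also say that 38 was reached from the unrounded value, since 34.67 × 1.1 = 38.14, which is 38 to the nearest integer. The text does not show this; it states 34 and adds the allowance to the calculated size. On either route, 10% loss from 38 leaves 34.2.

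A reader might treat the normal quantiles under a t label as a second error. The documents do not support that. The plan prints the values it used, and using them in this closed formula is a common approximation.

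**Conclusion.** The point holds as a minor arithmetic correction. The plan's formula and inputs require 35 per group, not 34, and following that through would give 39 per group and 78 in total, two participants more than planned. With the full 10% loss, power is 89.4% (normal approximation) or 88.5% (t-test) instead of 90%.

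A reader might infer that the trial as planned does not deliver 90% power. That is too strong. At 38 evaluable per group, power is 91.7% by the t-test. It drops below 90% only from three losses per group by the t-test, or four by the normal approximation.

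A reader might also take these percentages as the power of the planned analysis. They are not. They assume S = 2.75, δ = 2.14, two-sided α = 0.05, equal groups and an independent two-group comparison on MMSE values. The plan collects MoCA and names a paired t-test, so the power of that analysis cannot be derived from this calculation.

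**What to change.** In item 7, Objective No. 3:

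1. Correct the requirement to 35 per group, showing 34.67 rounded up.
2. Keep the target of 76 (38 per group), but do not describe it as 35 plus a full 10%, since 38 leaves room for three losses per group by the plan's formula.
3. State that, after the budgeted 10% loss, 34 evaluable per group give about 89% power (88.5% by two-sample t-test) under the assumed S and δ.
4. Say that this figure is for an independent two-group comparison on the MMSE values used for planning, not for the paired t-test on MoCA.
5. Optionally, note that 1.96 and 1.28 are normal quantiles used as an approximation.

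The cost is a few lines of text and a slightly lower stated power, with no extra recruitment. Raising the target to 78 would satisfy the plan's formula after 10% loss, but 35 evaluable per group still give 89.4% by the t-test. Reaching 90% by that test needs 36, which is 40 per group and 80 in total with the allowance (36 × 1.1 = 39.6; 36 / 0.9 = 40). A gain of this size does not call for a change of target.

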1) Research design: Quasi-Experimental Design (Non-randomized controlled trial) with experiment and control groups for comparison. Because of ethical considerations on older adults for logistical and economical wise, easy to travel, practical, less budget. Similar studies involving rehabilitation or behavioural interventions in real-world settings have widely used quasi-experimental designs. Studies by MA Handley(2018) and AD Harris (2006) demonstrated reliable outcomes using this approach.

2) Study area: Liaoning Province, China.

3) Study population

i) Reference population: Older adults living in Liaoning.

ii) Source population / sampling pool: Elderly care institutions and rehabilitation centers, Liaoning Province.

iii) Target population: Jinzhou Comprehensive Elderly Care Institution and Rehabilitation Center, Liaoning Province.

iv) Sampling frame: List of members from the two elderly care institution and rehabilitation center; Jinzhou Pension Comprehensive Service Center (JPCSC)), and Jinzhou Rehabilitation Hospital (JRH), Liaoning Province.

4) Subject criteria

Objective No. 1 and 2: To develop and validate the psychomotor rehabilitation nursing plan through content/face validation using the Delphi method.

Inclusion criteria:

- i) Professionals with ≥ 5 years of experience in geriatric care, neurological rehabilitation, cognitive rehabilitation, or psychomotor therapy.
- ii) Academic researchers with publications in related fields.
- iii) Intermediate professional title or above.
- iv) Willingness to participate in multiple Delphi rounds and provide informed feedback.

Exclusion criteria:

- i) Experts without sufficient relevant experience.
- ii) Those unable to commit to the Delphi process.

Objective No. 3: To evaluate the effectiveness of the psychomotor rehabilitation nursing plan in enhancing cognitive function among older adults with mild cognitive impairment. (Experimental and control group)

Inclusion criteria:

- i) Older adults are aged 50 years and above.
- ii) Subjective cognitive complaints from the individual or caregiver.
- iii) Screening for MCI using the Mini-Cog scores between 0-2 (SN Abayomi, 2024).
- iv) Basic language communication, listening, speaking, and understanding skills.

- v) Ability to provide informed consent.

Exclusion criteria:

- i) Diagnosed with severe psychiatric conditions (e.g., schizophrenia, major depressive disorder).

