Purposive sampling. Potential participants will be identified through a literature review, existing academic contacts, and a web search for cognitive training programs (for MCI or Neurology or other conditions) and the respective scientific teams. After being evaluated in accordance to the point system previously described, professionals who met the inclusion criteria (2 points or more) will be invited to participate by email. In the initial questionnaire, they will be asked to recommend other professionals who they considered to be experts in the field. Recommended professionals who met the inclusion criteria will be contacted and invited to join the expert panel.

PHASE 2 (Quasi-Experimental design for PMT rehabilitation nursing interventional study)

This experimental method will be used in Quasi-Experimental Design (Non-randomized controlled trial) with experiment and control groups for comparison. Ethics consideration on older adults which would psychologically and emotionally impact in case not selected for experimental group. This research will be carried out in Liaoning Province of China. The rehabilitation nursing intervention will be carried out for older adults with MCI admitted in two China elderly care institutions which the name is Jinzhou Pension Comprehensive Service Center (JPCSC) and Jinzhou Rehabilitation Hospital (JRH). Because of ethical consideration on older adults for logistical and economical wise, easy to travel, practical, less budget. So the experimental group is JRH, and the control group is JPCSC. Purposive sampling, whereby older adults with MCI will be selected and invited to participate the study.

The PMT rehabilitation nursing intervention plan

From Table in the literature review, we can see that most interventions lasted for 3 months. Therefore, older adults will be engaged in a 12-week PMT rehabilitation nursing plan involving 2 phases of relaxation and breathing exercises, face exercises, hand exercises and mind exercises to promote cognitive health. The experimental group will be given interventions, twice a week every Tuesday and Thursday 9-10 am along with the study

intervention. Meanwhile, the control group will be given a standard health education on cognitive health.

Table The Mind-body Exercise of Psychomotor Rehabilitation Nursing Plan

Week	Phase	Intervention methods	Assessment

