2.6 Phase 2 -Task 1	Do relaxation and breathing exercises before and after exercise (10 minutes).			
2.7 Phase 2 -Task 2	Hand muscle training/flexibility training/hand-eye coordination/improved circulation: The older adults held and rotated two balls with one hand according to instructions (10 minutes).			
2.8 Phase 2 -Task 3	Hand fine training/flexibility training/hand-eye coordination/endurance and concentration training (10 minutes).			
2.9 Phase 2 -Task 4	Hand-eye coordination training/cognitive ability training/fine skills training/teamwork and social interaction training (10 minutes).			
2.10 Phase 2 -Task 5	Carry out upper limb gymnastics exercises with music to improve limb motor function (20 minutes).			

Objective No. 3: To evaluate the effectiveness of psychomotor rehabilitation nursing plan in enhancing cognitive function among older adults with mild cognitive impairment.

Data entry and analysis will be performed using SPSS 28.0 software. Descriptive statistics will be used to summarize the general information of older adults. Numerical data will be presented as mean (SD) or median (IQR) based on their normality distribution. Categorical data will be presented as frequency (%). The comparison of scores of various scales are based on paired t-test statistical methods. The P value <0.05 will be considered to indicate statistically significant with 95% confidence interval (CI).

Expected result (Dummy Table): The effect assessment of the PMT rehabilitation nursing plan

Table Comparison of cognitive status between two groups ($\bar{x} \pm s$, scores)

Assessment	Before (n = 76)	After (n = 76)	Diff (95% CI)	t	P
Orientation					
Registration					
Attention and Calculation					
Recall					
Language and Praxis					
MoCA total score					

[figure not shown]
Table Comparison of psychological status between two groups ($\bar{x} \pm s$, scores)

Assessment	Before (n = 76)	After (n = 76)	Diff (95% CI)	t	P
Positive scale					
General psychopathology scale					
Negative scale					

Table Comparison of mental rehabilitation status between two groups ($\bar{x} \pm s$, scores)

Assessment	Before (n = 76)	After (n = 76)	Diff (95% CI)	t	P
Mood-related signs					
Behavioral disturbance					
Cyclic functions					
Ideational disturbance					

Study flowchart

Gantt chart & milestone

Research Activities	2024				2025				2026			
	Jan-Mar	Apr-Jun	Jul-Sep	Oct-Dec	Jan-Mar	Apr-Jun	Jul-Sep	Oct-Dec	Jan-Mar	Apr-Jun	Jul-Sep	Oct-Dec
Preliminary discussion												

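### Phase 2 enrols by purposive sampling at sites whose arm is already known, with no rule on who is approached or in what order, although member lists are the stated sampling frame

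*Combined protocol and SAP*

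**What the plan says.** All references are to the Methodology section of the combined protocol and SAP.

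- Item 1 describes the design as "Quasi-Experimental Design (Non-randomized controlled trial) with experiment and control groups for comparison".
- Item 3 gives the sampling frame as "List of members from the two elderly care institution and rehabilitation center", and names JPCSC and JRH.
- Item 4 gives one set of inclusion and exclusion criteria for both groups, including age 50 or over, a cognitive complaint and a Mini-Cog score of 0 to 2.
- Items 5 and 9 tie the arm to the site: "So the experimental group is JRH, and the control group is JPCSC".
- Item 8 reads "8) Sampling method: Purposive sampling". Item 9, Phase 2, repeats it: "Purposive sampling, whereby older adults with MCI will be selected and invited to participate the study".
- Item 11 gives the analysis for objective 3: "The comparison of scores of various scales are based on paired t-test statistical methods". No covariate adjustment is mentioned, although item 10 collects age, education, chronic disease and baseline MoCA.

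The plan does not say who selects, whether all eligible members are approached, in what order, or what happens if more than 38 people qualify at a site. It describes no screening log.

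**The concern.** When the arm is set by site, nothing is concealed from the person who invites. In a non-randomised comparison, any freedom in choosing among eligible people can then favour one arm. A fixed order of approach would remove that freedom, and the named sampling frame makes such an order possible.

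The plan also contains a reason why discretion might not act alike at the two sites. Item 4 withdraws participants for non-compliance and gives missing more than 25% of sessions as the example. The experimental programme has 2 × 12 = 24 sessions, while controls receive standard health education with no stated schedule. A recruiter at JRH has a reason to prefer people who are likely to attend; no matching reason is stated for JPCSC. This is a possible mechanism, not evidence that it will operate.

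At stake is whether a difference between groups at 12 weeks reflects the programme or the kind of person invited to it. This is additional to the confounding that comes from having one site per arm.

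**Working it through.** **1. Is there an invitation rule?** Phase 1 and Phase 2 both use purposive sampling, so their wording can be compared. For the Delphi panel (item 9, Phase 1), the plan includes all professionals who score at least 2 points, and says that those who qualify will be invited. For Phase 2 it gives eligibility criteria and says that people will be selected and invited. It has no all-eligible rule and no order. The summary speaks of older adults in a certain period, which hints at enrolment over a time window but is not a consecutive rule.

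**2. Do the stated reasons cover it?** Items 1 and 9 cite logistics, travel, budget and the emotional effect of not being chosen for the experimental group. These are reasons to allocate by site. None is a reason for discretion within a site.

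**3. The plan's own sample size (item 7).** Inputs: S = 2.75 and δ = 2.14 (both MMSE), 1.96 and 1.28.

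n = 2 × [(1.96 + 1.28) × 2.75 / 2.14]² = 34.67 per group.

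The plan states 34, and 34 × 1.1 = 37.4, which rounds up to 38 per group and 76 in total. The figure reproduces within rounding (34.67 rounded up would be 35). The order of invitation does not enter this formula, so the fix leaves 76 unchanged.

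**4. Illustration of size.** The documents give no input for the amount of bias, so b below is an assumption. Suppose there is no true effect and selection produces a difference of b points in an unadjusted, two-sided between-arm z-test at 5%, with SD 2.75.

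SE = 2.75 × √(2/n), which is 0.667 for n = 34 and 0.631 for n = 38.

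P(significant) = 1 − Φ(1.96 − b/SE) + Φ(−1.96 − b/SE).

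| b (points) | b / 2.14 | n = 34 per arm | n = 38 per arm |
|---|---|---|---|
| 0.25 | 12% | 7% | 7% |
| 0.50 | 23% | 12% | 12% |
| 0.75 | 35% | 20% | 22% |
| 1.00 | 47% | 32% | 35% |

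**5. What the table does not cover.** The planning values are on the MMSE, while the cognitive outcome is MoCA. The named test is a paired t-test, not a between-arm test. Suppose selection raises one arm by a points at both visits and adds a further c points at 12 weeks. A between-arm comparison of 12-week scores is then biased by a + c, but a comparison of changes is biased by (a + c) − a = c. A constant advantage in level cancels from a comparison of changes; an effect of selection on change does not. The documents give neither a nor c.

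**The case against.** The strongest reply is that purposive here simply means chosen by stated criteria. Phase 1 uses the word that way, Phase 2 has explicit criteria, and one sampling method and one set of criteria apply to both sites. Selection that acts alike at both sites mainly limits generalisability and does not bias the difference. If the number of eligible members at each site is close to 38, little room for choice remains; the documents do not give that number.

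Much of this stands. A reader might infer that participants are hand-picked, or that fitter or keener people will be chosen for the PMT site. The text says neither: it leaves discretion open and does not show that discretion will be used differently by site. A reader might also take the error rates above as those of this trial. They are not, because they belong to an unadjusted between-arm test on MMSE values. Nor do the documents support the claim that no analysis could help. Baseline cognition, age, education and chronic disease are recorded and could be adjusted for. Motivation to join and cooperation are at most touched on by some PANSS items and would be poorly captured.

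What the reply does not answer is that Phase 2 lacks the include-all-who-qualify rule that Phase 1 has, in the phase where the arm is known at invitation and the effectiveness claim is made.

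**Conclusion.** The point holds as a gap that leaves avoidable discretion. Phase 2 specifies purposive selection with the arm known in advance and no rule for who is approached, while naming a frame from which such a rule could be written. This could bias the group comparison if discretion is exercised differently at the two sites. Whether it would, and by how much, cannot be determined from the documents.

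The table shows only that a modest imbalance would matter in an unadjusted between-arm comparison: 0.25 to 1.0 point is 12% to 47% of the planned difference, and gives roughly 7% to 35% false positives with 38 per arm. It rests on an assumed b, an SD of 2.75 carried over from the MMSE, and a test that the plan does not name.

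The change is worth making because it is cheap. It is not the main threat to the comparison: with one site per arm, site confounding remains whatever the order of invitation.

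**What to change.** Replace purposive sampling in items 8 and 9 (Phase 2) with the same written rule at both sites. Put each member list in random order, or screen consecutively; apply the item 4 criteria in that order; and invite every eligible person until 38 are enrolled at that site. Keep a screening log and report, by site, the numbers screened, eligible, declined and enrolled.

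The cost is protocol wording, a log, more Mini-Cog screening (the frame lists members, not members with MCI) and slower recruitment. The documents do not show whether existing staff could absorb this. The target of 76 is unaffected.

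The change removes recruiter discretion over whom to approach. It does not remove self-selection through consent, since invitees still decide knowing what their site offers, but the log makes the refusal rates by site visible. Nor does it remove site confounding. Measured baseline differences still need an adjusted between-group analysis, for example 12-week MoCA by group with baseline MoCA, age and education as covariates, reported with the caveat that site and arm cannot be separated.
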